The study population of Pfizer-BioNTech COVID-19 mRNA vaccine recipients will be described in terms of demographic and health history characteristics, along with vaccination characteristics such as number of doses received and interval between doses. The incidence rates of medically attended safety events of interest will be estimated in the primary safety dataset of participants who enroll within 2 days of vaccination. Rates will also be estimated for the overall study population and within subcohorts of interest such as pregnant vaccine recipients, immunocompromised participants, and within age-categories. The final analysis will also be conducted for the following additional subcohorts of interest: Pfizer-BioNTech vaccine only; Heterologous vaccination (Pfizer-BioNTech booster[s] only; Heterologous primary course; Other combination heterologous vaccine course/booster). For events with a

sufficient number of cases, the observed rate will be compared with expected rates where available from historical or concurrent rates as reported in the scientific literature or other sources including those reported by the EMA-funded COVID-19 vaccine monitoring ACCESS program. For selected endpoints, such as those with acute onset and a definable risk window, a SCRI analysis will be implemented if case counts are sufficient. All statistical analyses will be described in a statistical analysis plan (SAP).

Milestones:

Data collection is planned to start 31 August 2021. Twice yearly interim reports are planned until 01 March 2024, with the final study report planned for 30 September 2024.

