6. MILESTONES

Milestone	Planned date
Start of data collection	31 August 2021
Registration in the EU PAS register	08 June 2021
Progress report	01 September 2021
Interim Reports	01 March 2022 01 September 2022 01 March 2023 01 September 2023 01 March 2024
End of data collection	31 October 2023
Final study report	30 September 2024

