7. RATIONALE AND BACKGROUND

7.1. Background

In December 2019, a novel coronavirus (severe acute respiratory syndrome coronavirus 2 [SARS-CoV-2]) was first identified by public health officials in China. The World Health Organization (WHO) declared the SARS-CoV-2 outbreak and associated disease (Coronavirus disease 2019 [COVID-19]) a global pandemic in March 2020 (1). Despite public health efforts, the incidence of COVID-19 has continued to rise, largely affecting middle-aged persons with worsening clinical sequelae linked to increasing age and comorbid conditions (e.g. cardiovascular disease, diabetes, and chronic lung disease) (2).

Given the rapid transmission of COVID-19 and incidence of disease in Europe, the rapid development of an effective vaccine is of utmost importance. Pfizer's and BioNTech's BNT162b2 vaccine candidate safety and efficacy are being tested worldwide in a diverse sample of subjects; however, individuals who are pregnant or immunocompromised are not included in the pivotal study, which has incorporated inclusion of subjects between 12 and 15 years of age (3). The Pfizer-BioNTech COVID-19 messenger ribonucleic acid (mRNA) vaccine has been granted conditional marketing authorization by the European Medicines Agency (EMA) for the prevention of SARS-CoV-2 infection. This study is part of a larger active surveillance plan to provide comprehensive information on real-world safety of the Pfizer-BioNTech COVID-19 mRNA vaccine within a 2-year period following vaccination of individuals within the European Union (EU).

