9.3.1. Safety Outcome Definitions

Data on medically attended safety events of interest will be collected from the time of participants' enrolment into the study until death, withdrawal of consent, loss to follow-up or end of study period, whichever occurs first.

Medically attended safety events of interest in this study are listed in Table 2. These events are based on the AESI lists developed by ACCESS and SPEAC/Brighton Collaboration, which consists of events previously identified with immunization in general (e.g. anaphylaxis, GBS), with vaccine platforms relevant to COVID-19 vaccine development, or with theoretical concerns based on immunopathogenesis or viral replication during wild type disease (4, 5).

Participant reported medically attended safety events of interest will be followed up with the treating HCPs or through medical record documentation if needed to validate or establish the diagnosis associated with the event and validate the occurrence of a safety event of interest, or other clinically significant event. Additional safety events may be added as endpoints based on emerging findings from clinical studies, spontaneous reports, literature or updates in guidance.

Table 2. Medically attended safety events of interest^a

Body System	Safety Event
Neurologic	Generalized convulsion/ seizure
	Guillain-Barré Syndrome (GBS)
	Aseptic meningitis
	Encephalitis / Encephalomyelitis
	Other acute demyelinating diseases
	Transverse myelitis
	Multiple sclerosis
	Optic neuritis

090177e1991e3913\Approved\Approved On: 18-Jan-2022 22:29 (GMT)

Table 2. Medically attended safety events of interest^a

Body System	Safety Event
	Bell's palsy
	Acute disseminated encephalomyelitis
Immunologic	Anaphylaxis
	Vasculitides*
	Arthritis and arthralgia
	Multisystem inflammatory syndrome in adults (MIS-A)
	Kawasaki disease
	Fibromyalgia
	Autoimmune thyroiditis
COVID-19	Severe COVID-19 disease * **
	Acute respiratory distress syndrome
	Microangiopathy*
	Heart failure and cardiogenic shock*
	Stress cardiomyopathy*
	Coronary artery disease*
	Arrhythmia*
	Deep vein thrombosis
	Pulmonary embolus
	Cerebrovascular stroke
	Limb ischemia*
	Hemorrhagic disease*
	Acute kidney injury*
	Acute liver injury
	Chilblain-like lesions
	Single organ cutaneous vasculitis*
	Erythema multiforme*
	Anosmia, Ageusia
	Acute pancreatitis

090177e1991e3913\Approved\Approved On: 18-Jan-2022 22:29 (GMT)

Table 2. Medically attended safety events of interest^a

Body System	Safety Event
	Rhabdomyolysis

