9.4.2. Weekly, monthly, and long-term follow-up, through 24 months following the index date vaccine dose

The following data will be collected directly from participants at pre-specified follow-up points outlined in the data collection schedule (further details in [Annex 3](#)):

1. Pregnancy status (female participants of childbearing potential only), and pregnancy outcomes (as applicable).
2. Details of medically attended safety events of interest, including laboratory confirmed diagnosis of COVID-19, since the last follow-up.
3. Any changes in contact information.
4. Changes in preferred follow-up method – telephone interview or web/app-based questionnaire.
5. Discontinuation data will be collected for all enrolled participants at the time of discontinuation:
 - Date of discontinuation.
 - Number of vaccine doses received at the time of discontinuation.
 - Reason for discontinuation.

Data on reactogenicity will be collected only during week 1 following each Pfizer-BioNTech vaccine dose.

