To answer the first secondary objective, the observed rate of events will be compared with expected rates using the Observed to Expected (OE) analysis approach (6). The core principle of OE analysis is to estimate the expected number of coincidental cases of medically attended safety events of interest, under the assumption of no association with the vaccine. Expected numbers are then compared with the number of cases actually reported in vaccine recipients. The expected background incidence rate of a particular safety event of interest is the number of new cases occurring naturally in the population, expressed in person-time. The comparison of OE number of medically attended safety events of interest will be expressed as the ratio of the observed over the expected: an OE ratio equal to 1 means that the observed number of cases equals the expected number of cases, whereas an OE ratio greater than 1 signals an excess of risk in the vaccinated population. The statistical uncertainty of the OE analysis will often be driven by the observed number of cases, which are often rare events. To deal with this statistical uncertainty, a 95% Poisson exact confidence interval (95% CI) will be calculated (7). If the lower limit of the 95% CI of the OE ratio is greater than 1, the observed value is considered significantly higher than expected (Figure 2, case [a]). If the upper limit of the 95% CI of the OE ratio is lower than one, the observed value is considered significantly lower than expected (Figure 2, case [b]). If the 95% CI contains 1, then the observed and the expected numbers will not be considered significantly different (Figure 2, case [c]).

[figure not shown]
Figure 2. Observed to Expected (OE) Ratios and 95% Confidence Intervals (CIs)

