Expected background rates of safety event of interest will be obtained from the EMA-funded COVID-19 vaccine monitoring ACCESS program (8). The ACCESS program is generating background incidence rates of AESI for COVID-19 vaccines over the period 2017 to 2020 from 10 healthcare databases in 7 European countries (8). The analysis in this study will include age-categories in line with the published incidence rates from ACCESS (18-29; 30-39; 40-49; 50-59; 60-69; 70-79; 80+). For safety event of interest which are not expected to be investigated through the ACCESS program, expected rates will be obtained from historical or concurrent rates reported in the literature, including from reports or data available through health authorities or large databases where possible (9, 10). This OE analysis has been favorably compared with other methods for active surveillance of vaccine safety (10).

For selected endpoints, such as those with acute onset and a defined risk window (listed in Annex 4), a SCRI analysis will be implemented if case counts are sufficient. SCRI analysis, described by Farrington (11, 12, 13), compares incidence rates between “risk” and “control” time periods (intervals) among vaccinated individuals, under the assumption that the risk of onset of a safety event of interest on a day during the risk period is the same as that on a day during the control period. The risk interval is a biologically plausible window of time following a vaccine when a safety event of interest could be caused by the vaccine (Figure 3).

Figure 3. Self-Controlled Risk Interval (SCRI) analysis: defining risk and control intervals

090177e1991e3913\Approved\Approved On: 18-Jan-2022 22:29 (GMT)

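### The observed-to-expected (OE) analysis sets 2021–2023 follow-up, with SARS-CoV-2 infection left in, against mostly pre-pandemic 2017–2020 rates, which pushes the ratio upward for infection-related events

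*Protocol*

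**What the plan says.** - **Source of expected rates.** Protocol 9.7 names ACCESS, which supplies "background incidence rates of AESI for COVID-19 vaccines over the period 2017 to 2020 from 10 healthcare databases in 7 European countries". For events that ACCESS is not expected to study, "expected rates will be obtained from historical or concurrent rates reported in the literature". Table 5 repeats this order: literature rates, historical or concurrent, only where ACCESS rates are unavailable.
- **Observed period.** The abstract states: "Data collection is planned to start 31 August 2021". Section 6 gives the end of data collection as "31 October 2023".
- **Time at risk.** Section 9.7 ends it at the next Pfizer-BioNTech dose, death, withdrawal, loss to follow-up, 24 months or end of study. Infection is not in the list. The one censoring sensitivity analysis named, which is optional, is at any COVID-19 vaccine dose.
- **Reading rule.** Section 9.7 states that "an OE ratio greater than 1 signals an excess of risk in the vaccinated population". A lower 95% limit above 1 is called significantly higher than expected.
- **Outcomes.** Table 2 in 9.3.1 has a COVID-19 block that begins with "Severe COVID-19 disease" and includes ARDS, deep vein thrombosis, pulmonary embolus, stroke, acute kidney injury and anosmia/ageusia.
- **Infection data.** Section 9.4.2 collects medically attended events "including laboratory confirmed diagnosis of COVID-19, since the last follow-up". The only analytic use that 9.7 gives these infections is description by the VAED case definitions.

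**The concern.** Section 9.7 says that OE estimates how many coincidental cases would occur if the vaccine had no association with the event. That requires expected rates from a setting like the one observed in everything but vaccination. Here the settings differ in a cause of many of the outcomes. Section 7.1 dates the virus itself: "In December 2019, a novel coronavirus" was first identified, and the pandemic was declared in March 2020. Most of the reference period therefore precedes it, and all of the follow-up comes after it.

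The protocol makes the link to infection itself. Section 9.3.1 says that part of the event list rests on what the wild-type virus does when it replicates, and Table 2 groups a block of events under COVID-19. An event caused by infection during follow-up counts as observed but has little counterpart in the expected number. At stake is the first secondary objective, whether vaccine recipients have increased risk. Section 9.9 mentions neither the period mismatch nor infection.

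**Working it through.** **1. The two periods.** Reference: 2017 to 2020, 48 months. Pandemic part, March to December 2020: 10 months, and 10/48 = 21%. Observed: 31 August 2021 to 31 October 2023, 26 months. Overlap: none.

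**2. Person-years, checked against the plan's own table.** The protocol states no expected count for the OE analysis, so I take person-years from section 9.5. With 13,334 enrolled and 25% dropout spread evenly over two years, 13,334 × 2 × (1 − 0.25/2) = 23,334.5 person-years. Exact Poisson intervals on this figure reproduce all eight 25% rows of Table 4 to rounding. For example, 10 per 10,000 gives 6.2 to 14.8 (table: 6 to 15), and 500 gives 471.8 to 529.7 (table: 472 to 530).

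**3. Push on the ratio with no vaccine effect.** Let *i* be infections per person-year, *w* the days after infection with raised risk, and *R* the rate ratio in that window. The documents give none of these, so all are assumptions. With no infection in the reference:

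OE = 1 + *a*, where *a* = *i* × (*w*/365) × (*R* − 1)

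- Low (0.1, 30 days, 5): 1 + 0.1 × 0.0822 × 4 = 1.03
- Middle (0.3, 30 days, 10): 1 + 0.3 × 0.0822 × 9 = 1.22
- High (0.6, 30 days, 20): 1 + 0.6 × 0.0822 × 19 = 1.94

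**4. With 2020 infections in the reference.** Suppose the rates are pooled over four equal years and 2020 had the same infection effect. Then OE = (1 + *a*)/(1 + *a*/4):

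- Low: 1.033/1.008 = 1.02
- Middle: 1.222/1.055 = 1.16
- High: 1.937/1.234 = 1.57

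**5. Chance that the lower 95% limit exceeds 1 when the vaccine does nothing.** Expected count = reference rate × 23,334.5 person-years; exact Poisson.

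| Reference rate per 10,000 PY | Expected count | True OE 1.00 | 1.03 | 1.16 | 1.22 | 1.94 |
|---|---|---|---|---|---|---|
| 5 | 11.7 | 1.6% | 2.2% | 6% | 9% | 74% |
| 10 | 23.3 | 2.2% | 3.3% | 11% | 17% | 96% |
| 50 | 116.7 | 2.4% | 5.3% | 38% | 63% | about 100% |
| 250 | 583.4 | 2.4% | 12% | about 95% | about 100% | about 100% |

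A longer window raises the ratio: 0.3 infections per person-year, 90 days and *R* = 5 give 1.30. All these figures assume OE over the whole follow-up. Table 2's footnote leaves risk windows to the SAP, and short windows would change them.

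**6. Censoring alone is not enough.** If follow-up is censored at infection but the reference keeps 2020, the step 4 inputs give 1/1.055 = 0.95 in the middle case and 1/1.234 = 0.81 in the high case. That is a downward bias, which could hide a real risk. Infection has to be removed from both sides.

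**The case against.** **Expected rates and sensitivity analyses belong to the SAP.** Section 9.7 does leave the rate values and sensitivity analyses there. But the order of sources, the 2017–2020 period and the end of time at risk are protocol text, and a SAP that follows them inherits the mismatch.

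**Concurrent rates are already allowed.** The abstract is looser and lists historical or concurrent rates side by side with ACCESS. Section 9.7 and Table 5 are specific, however, and confine concurrent rates to events without ACCESS rates. If ACCESS lacks some infection-specific events, the problem is avoidable for those. The protocol does not say which they are.

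**The analysis is exploratory, and other biases pull the other way.** Both are true. Section 9.5 rules out formal hypothesis testing for secondary endpoints, and the abstract limits OE to events with enough cases. Participants who cannot be contacted stay in follow-up (10.3) and events may be forgotten (9.9), and both lower observed rates. The net direction is therefore not established, although the contribution of infection is upward. The self-controlled analysis runs only if counts suffice and does not correct the OE ratio.

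**Two stronger readings that the documents do not support.**
- A reader might infer that COVID-specific events are inflated at least fourfold because only one of four reference years had the virus. That needs pooled rates, ACCESS coverage of the event, no cases in 2017–2019 and a study rate no lower than in 2020. The protocol states neither of the first two. The third is true by definition for severe COVID-19 but not shown for anosmia. Vaccine protection would break the fourth.
- A reader might infer that the questionnaire in 18.1.3 captures only listed diagnoses. It also asks about any other diagnosis. The real gap is narrower: both questions follow only if unplanned medical care is reported, so an infection without such care is not asked about.

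**Conclusion.** The point holds as an upward push of unknown size on the OE ratio for outcomes that infection can cause. The period mismatch, the absence of infection from the censoring rules and the reading of OE above 1 are all fixed in section 9.7.

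Under the assumed inputs, the ratio with no vaccine effect is about 1.03 to 1.94 if the reference contains no infection, and about 1.02 to 1.57 if 2020 contributes a quarter of it with the same infection effect. It should be largest for infection-specific events such as severe COVID-19. For rare events weakly linked to infection it is negligible, and the false-flag rate stays near its nominal level.

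It would go too far to conclude that every such event will be flagged as a vaccine risk. The size rests on assumptions, the SAP may set short risk windows, and under-reporting may offset the push. The change should be made, but it does not touch the primary objective.

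**What to change.** In section 9.7:

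1. For Table 2 outcomes that arise essentially only from infection (severe COVID-19 and others so classified), compute no OE ratio against 2017–2020 rates. Report incidence, or compare with calendar-concurrent rates only.
2. For the other events, keep the planned OE and pre-specify a sensitivity OE beside it. Censor events and person-time at the first reported laboratory-confirmed SARS-CoV-2 infection after the dose, and use 2017–2019 reference rates where ACCESS gives rates by year, so that infection is absent from both sides.
3. State with the reading rule, and in 9.9, that an OE above 1 in the uncensored analysis may reflect infection.

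Optionally, add to 18.1.3 a positive-test item with its date, asked whether or not the participant reports unplanned care.

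**Cost.** A paragraph in 9.7, a sentence in 9.9 and, if adopted, one questionnaire item. The sensitivity analysis uses data already planned. It has fewer person-years, and its censoring may be informative because infection follows vaccination and may be affected by it. Without the extra item it misses infections that did not lead to medical care. It should therefore stand beside the planned OE, not replace it.

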9.7.1. Handling of missing data

It is optimal to prevent missing data, to the extent possible, through strategies set forth in the design and conduct of a study. For the current study, we will aim to minimize missing information by:

- Following the larger active surveillance plan, aiming to actively engage participants to provide information on safety events.
- Ensuring that primary variables of interest are those that are routinely collected as part of real-world clinical care and are available via medical charts, physician and/or participant reporting, as appropriate.
- Collecting only critical data elements (i.e. variables aligned with the study objectives) to minimize site/participant burden.

- Including "not applicable", "not done" on CRFs to differentiate these from values that are truly unknown.
- Training of sites and data abstractors regarding data collection; setting reporting windows around a target timepoint.
- Planning for random missingness, loss to follow-up, and attrition in the sample size calculations.

Should missing data occur, the data will be analyzed as they are recorded in the study eCRFs. Counts of missing data will be reported for demographic and medical history variables, as outlined in [Section 9.4.1](#). Missing safety data will not be imputed. Handling of missing data, including partial/completely missing dates, will be described in the SAP.

9.8. Quality control

A study monitoring plan that is appropriate for the study design will be developed and implemented. IQVIA will provide training on the conduct of the study to all relevant staff involved in the study. Representatives of Pfizer's quality assurance unit/monitoring team and competent regulatory authorities must be permitted to inspect all study-related documents. Audits may be conducted at any time during or after the study to ensure the validity and integrity of the study data.

9.9. Limitations of the research methods

This is a non-interventional, multinational, multi-center PASS to further document the safety profile of participants vaccinated with the Pfizer-BioNTech COVID-19 mRNA vaccine. Participants will be followed for up to 24 months after their vaccine dose.

The time frame of 24 months post-vaccination will allow evaluation of the long-term safety profile of the Pfizer-BioNTech COVID-19 mRNA vaccine in a real-world population. To reduce the likelihood of sampling bias, broad inclusion criteria and consecutive participant selection will be applied.

Recruiting participants soon after vaccination is important to prevent over-representation of participants who elect to enroll only after experiencing an event. The study recruitment strategy will encourage enrolment within 2 days of vaccination, but in consideration of the enrolment goal of up to 10,000 participants, diverse and changing local vaccine roll-out strategies, and to provide potential participants enough time to inform themselves fully before consenting, only enrollment within 5 days of vaccination will be eligible.

There is potential for loss to follow-up prior to study completion. To reduce the likelihood of loss to follow-up, active monitoring of participants will be employed. For participants who discontinue the study prematurely, the reason(s) for discontinuation will be recorded. The sponsor will aim to minimize missing information by the measures outlined in [Section 9.7.1](#).

There is also the potential for recall bias where participants may not remember or report events that occurred in between the questionnaire intervals. This is likely to be minimized by focusing on serious events and hospitalizations.

As participants may receive multiple vaccine doses during the study period, and may receive different types of COVID-19 vaccine, attributing outcomes to the relevant exposure period may be challenging. However, this will be mitigated through the collection of data on other vaccines (including date and manufacturer), including those received prior to the index date dose (e.g. to facilitate exclusion of participants who received the Pfizer-BioNTech COVID-19 mRNA vaccine as their second dose, who *did not* receive the same vaccine as their first dose), as well as through sensitivity analysis.

